[figure not shown]

## **ABSTRACT**

**Background:** Platelet-rich fibrin (PRF) is a second-generation platelet concentrate and has the potential to accelerate soft and hard tissue regeneration. The chorion membrane is a fetal tissue. It has been used for its exceptional wound-modulating properties. The aim of the present study was to evaluate and compare the clinical outcome of PRF and chorion membrane in the treatment of isolated Miller's class I or II gingival recession defects.

**Materials and methods:** A total of 50 recession defects were treated randomly with coronally advanced flap (CAF) along with PRF membrane (site A, n = 25 defects) or CAF with chorion membrane (site B, n = 25 defects). Clinical parameters measured at baseline, 1 month, 3 months and 6 months were recession depth (RD), recession width (RW), clinical attachment level (CAL), width of keratinised gingiva (WKG), plaque index (PI), gingival index (GI) and assessment of gingival biotype. Statistical analysis was performed to compare the treatment outcomes at the follow-up intervals.

**Results:** Six months after the surgery, statistically significant improvements in mean root coverage, RD, RW, CAL, WKT, PI and GI were observed in both groups. No statistically significant difference was found between the two groups for all of these parameters. The mean percentage of root coverage was  $86.76 \pm 13.76$  in the PRF group (site A) and  $82.89 \pm 15.65$  in the chorion group (site B) at six months post-operatively, with no statistically significant difference between them. The gingival biotype also showed a thick biotype in sites that had an initial thin biotype.

**Conclusion:** Both PRF and chorion membrane are adequate and predictable treatment modalities for the management of isolated recessed-type defects. Longitudinal studies are needed to confirm these findings.

**Keywords:** Coronally advanced flap, gingival recession defect, platelet-rich fibrin, root coverage, chorion membrane.

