## **Statistical Analysis**

Statistical analysis of the data was done using the statistical package for the social science (SPSS 22.0). The data was compiled using Microsoft excel sheet (windows 2007). For each variable the mean and standard deviation were calculated. The differences between the means were calculated using the Student's paired and independent t-test.  $p < 0.05$  was considered statistically significant.

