## **Unpaired (independent) 't' test:**

This test is applied to unpaired data of independent observations made on individuals of two different or separate groups or samples drawn from two populations, to test if the difference between the means is real or it can be attributed to sampling variability.

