### **Steps:**

1. As per the null hypothesis, assume that there is no real difference between the means of two samples.
2. Find the observed difference between means of two samples ( $\bar{X}_1 - \bar{X}_2$ )
3. Calculate the standard error of difference between the two means.

$$SE = \sqrt{\frac{1}{n_1} + \frac{1}{n_2}}$$

4. Calculate the 't' value

$$t = \frac{\bar{X}_1 - \bar{X}_2}{SE}$$

5. Determine the pooled degrees of freedom from the formula

$$d.f. = (n_1 - 1) + (n_2 - 1) = n_1 + n_2 - 2$$

6. Compare calculated value with the table value (table of 't') at particular degrees of freedom to find the level of significance.

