## **Paired “t” test:**

It is applied to paired data of independent observations from one sample only when each individual gives a pair of observations.

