### **Steps:**

1. As per the null hypothesis, assume that there is no real difference between the means of two samples.

2. Find the difference in each set of paired observations before and after  $(X_1 - X_2 = X)$

3. Calculate the mean of the differences  $(\bar{X})$

4. Work out the standard error of mean,  $SE = SD / \sqrt{n}$

5. Determine ‘t’ value

$$'t' = \frac{\bar{X}}{\text{Standard error of difference}}$$

6. Find the degrees of freedom  $(n - 1)$

7. Refer ‘t’ table and find the probability of ‘t’ corresponding to  $n - 1$  degree of freedom.

8. If the probability is more than 0.05, the difference observed has no significance, because it can be due to chance.

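### Does counting results by defect, without stating patients per arm or which t-test compared the arms, undermine the PRF-versus-chorion comparison?

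*Combined protocol and SAP*

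**What the plan says.** The Abstract allocates and counts by defect: "A total of 50 recession defects were treated randomly with coronally advanced flap (CAF) along with PRF membrane (site A, n = 25 defects"), and 25 at site B with chorion membrane. It calls the arms sites in one place and groups in another. For the comparison it reports: "No statistically significant difference was found between the two groups for all of these parameters". Its conclusion is that both membranes are "adequate and predictable treatment modalities for the management of isolated recessed-type defects".

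On method, the Statistical Analysis section says: "The differences between the means were calculated using the Student's paired and independent t-test". It does not say which test served which comparison. The general descriptions that follow give more. On the unpaired test: "This test is applied to unpaired data of independent observations made on individuals of two different or separate groups", with n1 + n2 - 2 degrees of freedom. On the paired test: "It is applied to paired data of independent observations from one sample only when each individual gives a pair of observations", and its worked steps include: "Find the difference in each set of paired observations before and after".

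The available text gives no number of patients and no number of defects per patient. Part of the document was not available to this review and may give both.

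**The concern.** An independent t-test assumes that every observation is independent of the others. Defects in the same mouth share oral hygiene, tissue type and healing, so their outcomes may be correlated. The labels site A and site B would suit a split-mouth design. If each patient gave one defect to each arm, an unpaired test would ignore the pairing and its interval would be too wide. If patients gave several defects to the same arm, the interval would be too narrow. At stake is how large a difference remains possible behind a non-significant result, and the Abstract prints no between-arm interval.

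A second oddity is on the case form. The person-level plaque index divides a single tooth's score by the number of teeth examined. The gingival index beside it first totals over teeth. Used literally with N equally scored teeth, the plaque formula gives a value N times too small.

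**Working it through.** **Inputs (Abstract).** Root coverage at six months: site A 86.76, SD 13.76, n = 25; site B 82.89, SD 15.65, n = 25. Significance level 0.05 (Statistical Analysis), taken as two-sided. Correlations (r), intraclass correlations (ICC) and numbers of shared patients are my assumptions; the available text gives none.

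**1. Reported result, independent test.**
- Difference = 86.76 - 82.89 = 3.87.
- SE = sqrt((13.76² + 15.65²)/25) = sqrt((189.34 + 244.92)/25) = 4.17.
- t = 3.87/4.17 = 0.93 on 25 + 25 - 2 = 48 df, p = 0.36.
- 95% CI = 3.87 ± 2.01 × 4.17 = -4.5 to 12.2.

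This agrees with the Abstract's non-significant finding. The SE in the Steps list is printed without a standard deviation. Taken literally it would be sqrt(2/25) = 0.28, giving t = 13.7. That contradicts the reported result, so it was evidently not the formula used.

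**2. One A and one B defect per patient (25 pairs, 24 df, critical t 2.06).** SE = sqrt((13.76² + 15.65² - 2r × 13.76 × 15.65)/25).

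| r | SE | 95% CI | p |
|---|---|---|---|
| 0 | 4.17 | -4.7 to 12.5 | 0.36 |
| 0.3 | 3.49 | -3.3 to 11.1 | 0.28 |
| 0.5 | 2.96 | -2.2 to 10.0 | 0.20 |

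The p-value reaches 0.05 only at r = 0.80. In this layout the independent test is conservative: its simulated type I error is about 2.0% at r = 0.3 and 0.7% at r = 0.5.

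**3. k patients per arm giving two defects, both in the same arm.** SE = 4.168 × sqrt(1 + 2k × ICC/25), df = 2(25 - k) - 2.

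| k | ICC | SE | 95% CI | p | Type I error of independent test |
|---|---|---|---|---|---|
| 5 | 0.3 | 4.41 | -5.1 to 12.8 | 0.39 | 6.3% |
| 5 | 0.5 | 4.57 | -5.4 to 13.1 | 0.40 | 7.2% |
| 12 | 0.3 | 4.73 | -5.9 to 13.6 | 0.42 | 8.4% |

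Type I errors in steps 2 and 3 come from 40,000 simulated trials per setting.

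**4. Defects randomised freely, whoever they belong to.** This is closest to the Abstract, which describes defects, not patients, as treated at random. With 50 defects split 25 to 25, three patient structures were simulated at ICC 0.3 and 0.5, again with 40,000 trials each: ten patients with two defects and thirty with one; 25 patients with two; and one to four defects each. The independent test's type I error was about 5% in every case, because some pairs fall within an arm and others straddle the arms, and the two effects offset. A smaller simulation (1,500 trials per setting) put interval coverage at 93% to 96% for one to four defects per patient; the low end arose when the treatment effect itself varied between patients.

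**5. One defect per patient.** Nothing changes: SE 4.17, CI -4.5 to 12.2.

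**6. Which layout and which test?** The Abstract calls the defects isolated, and the case form has a single entry each for recession depth, recession width and root coverage. Both fit one defect per patient. The Abstract makes two kinds of comparison: change within each arm, and A against B. The text describes two tests: one for separate groups, one for a single sample worked as before and after. The natural match is paired for change and independent for A against B.

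**The case for a change.** The strongest case for acting is that the reported result cannot settle the question. A paired test is also non-significant for any r below about 0.80, so the Abstract's wording does not reveal which test was run. The upper limit for root coverage runs from about 10 to 13.6 points across the layouts above, and a reader needs a valid interval to judge what the data leave open. Keying the analysis to the patient would give the independent test with one defect each and the paired test with one of each, at little cost. The same check cannot be made for the other outcomes, since the available text gives no means or SDs for them. If both arms shared a mouth, a person-level plaque or gingival index would be identical in both and could show no difference.

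The wish for the patient count, the layout, the test used and an interval stands as reporting detail. The claim that the analysis is wrong does not. It needs shared patients, for which the only cue is the site labelling. The too-narrow intervals need more: a patient's defects all falling in one arm, as under allocation by patient. Nor would a patient-level rerun be automatically correct: with so few patients it needs small-sample degrees of freedom, and the visible form has no field linking treated tooth and arm to the patient number.

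**Conclusion.** No change to the plan is needed. The ambiguity is a gap in the wording that an analyst would fill sensibly, using the independent test between arms and the paired test for change, unless the design is known to be split-mouth. With one defect per patient the interval of -4.5 to 12.2 is unchanged; with free randomisation by defect the independent test stays about nominal. If every patient gave one A and one B defect, a paired analysis would be the better choice, but the independent test would err on the cautious side. Only same-arm clustering makes it too liberal, at 6.3% to 8.4% under the assumptions tried, and there the difference is further from significance. The Abstract claims no equivalence, so no stated conclusion rests on the width of the interval. This rests on assumed correlations and on root coverage alone.

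The plaque index line is clerical: the gingival formula beside it shows the intended form, and nothing indicates that any result was computed as printed.

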## **Statistical Analysis**

Statistical analysis of the data was done using the statistical package for the social science (SPSS 22.0). The data was compiled using Microsoft excel sheet (windows 2007). For each variable the mean and standard deviation were calculated. The differences between the means were calculated using the Student's paired and independent t-test.  $p < 0.05$  was considered statistically significant.

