### **EXAMINATION:**

## GINGIVA:

### GINGIVAL WIDTH:

## GINGIVAL THICKNESS:

### RECESSION WIDTH:

### RECESSION DEPTH:

#### CLINICAL ATTACHMENT LEVEL:

% OF ROOT COVERAGE: (baseline RD - RD at 1, 3 or 6 months)/baseline RD.

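### The arm comparisons of RD, RW, CAL and WKG are not adjusted for baseline, although each was measured then; a 6-month ANCOVA would probably narrow the intervals, by an amount the documents do not fix

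*Combined protocol and SAP*

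**What the plan says.** The Statistical Analysis section gives the whole method for comparisons: "The differences between the means were calculated using the Student's paired and independent t-test". The pages after it explain the two tests in textbook terms. The unpaired test is for "independent observations made on individuals of two different or separate groups". The paired test is a before-and-after comparison: "Find the difference in each set of paired observations before and after". Neither contains a baseline term for the arm comparison, and no regression or covariance model appears in the statistical text.

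The abstract shows that the covariate exists: "Clinical parameters measured at baseline, 1 month, 3 months and 6 months were recession depth (RD", with RW, CAL and WKG in the same list. On the analysis it adds "Statistical analysis was performed to compare the treatment outcomes at the follow-up intervals", without saying whether follow-up values or changes from baseline were compared. The groups are "PRF membrane (site A, n = 25 defects) or CAF with chorion membrane (site B, n = 25 defects". The reported result is "No statistically significant difference was found between the two groups for all of these parameters".

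Only one outcome refers to baseline at all. This is percentage root coverage, which the Annexure III proforma defines from "baseline RD - RD at 1, 3 or 6 months)/baseline RD". There baseline RD is a denominator, not a covariate, and RW, CAL and WKG have no counterpart.

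**The concern.** Over randomisation, a t-test on 6-month values and a t-test on changes are both unbiased, so validity is not in question. The loss is in precision. A comparison of 6-month values leaves any chance baseline imbalance uncorrected. A comparison of changes subtracts the whole baseline difference, which is too much when the slope of follow-up on baseline is below 1. ANCOVA estimates that slope from the data.

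Precision matters here because the headline is a null result from 25 defects per arm. How much such a result says depends on the width of the interval, and the documents describe no interval for an arm difference. No baseline imbalance is documented, and none is assumed below.

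Plaque and gingival index are left out, because the proforma defines both a tooth score and a whole-person score and it is unclear which was compared.

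**Working it through.** **Inputs from the documents.** 25 and 25 defects; significance at p < 0.05 (taken as two-sided); 6-month root coverage 86.76 (SD 13.76) for PRF and 82.89 (SD 15.65) for chorion.

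**Inputs not given, so assumed.** r between baseline and 6 months; the SDs of RD, RW, CAL and WKG; whether sites A and B share a mouth. I use r = 0, 0.15, 0.3, 0.5 and 0.7.

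**Check on the reported result.** The plan states no sample-size or power figure to reproduce. For root coverage the difference is 86.76 − 82.89 = 3.87 points. SE = √((13.76² + 15.65²)/25) = √(434.26/25) = 4.17, so t = 3.87/4.17 = 0.93 on 48 df and p = 0.36. The 95% CI is 3.87 ± 2.0106 × 4.17, that is −4.5 to 12.2. This agrees with the reported non-significance. If the data are 25 within-mouth pairs with assumed within-pair correlation 0 / 0.3 / 0.5 / 0.7, the SE is 4.17 / 3.49 / 2.96 / 2.30 on 24 df and p = 0.36 / 0.28 / 0.20 / 0.11.

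**ANCOVA against a t-test on 6-month values, independent defects.** The CI width ratio is √(1 − r²) × √(1 + 1/46) × t₄₇/t₄₈. The second factor allows for chance baseline imbalance. The last is 2.0117/2.0106 for the lost degree of freedom. Together the last two come to 1.011. Break-even is where √(1 − r²) × 1.01137 = 1, at r = 0.15.

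**The same with 25 within-mouth pairs.** The 6-month A−B difference is regressed on the baseline A−B difference and compared with a paired t-test on 6-month values. The ratio is √(1 − r²) × √(1 + 1/22) × t₂₃/t₂₄, with penalty 1.025 and break-even r = 0.22. Here r is the correlation between the two A−B differences.

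**RD with values floored at zero.** Mean coverage of 83–87% leaves little recession at 6 months. Trials with no treatment effect were simulated (40,000 per cell) with an assumed quarter or half of 6-month values at zero. Here r is the correlation before flooring. ANCOVA type I error stayed at 4.9–5.1%.

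| CI width ratio at r = | 0 | 0.15 | 0.3 | 0.5 | 0.7 |
|---|---|---|---|---|---|
| Independent defects | 1.011 | 1.000 | 0.965 | 0.876 | 0.722 |
| RD, a quarter at zero | 1.011 | 1.001 | 0.970 | 0.891 | 0.757 |
| RD, half at zero | 1.011 | 1.003 | 0.977 | 0.913 | 0.808 |
| 25 pairs | 1.025 | 1.013 | 0.978 | 0.888 | 0.732 |

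**Detectable difference, 80% power, independent defects (noncentral t).** Unadjusted: 0.81 SD. With ANCOVA: 0.82 / 0.81 / 0.78 / 0.71 / 0.58 SD at the five values of r.

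**ANCOVA against a t-test on changes, independent defects.** With k = SD at 6 months / SD at baseline, the ratio is √(k²(1 − r²)/(k² + 1 − 2rk)) × 1.011.

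| CI width ratio at r = | 0 | 0.15 | 0.3 | 0.5 | 0.7 |
|---|---|---|---|---|---|
| k = 1 | 0.715 | 0.767 | 0.815 | 0.876 | 0.932 |
| k = 0.5 | 0.452 | 0.477 | 0.495 | 0.506 | 0.487 |
| k = 1.25 | 0.790 | 0.845 | 0.896 | 0.956 | 1.002 |

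The square root never exceeds 1, because k² + 1 − 2rk − k²(1 − r²) = (1 − rk)², which cannot be negative. The worst case is therefore the 1.1% penalty itself, reached when rk = 1.

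**The case against.** The strongest reply is that this is an efficiency preference on a finished analysis. The unadjusted test is acceptable under randomisation, and no figure for the gain comes from the documents. The one result that can be recomputed, root coverage, is left unadjusted here. All of that is true. It limits the claim to a probable gain of unknown size, but it does not remove a step that costs almost nothing in expected width.

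Second, showing only k = 1 and k = 0.5, with r stopped at 0.7, would flatter ANCOVA against change scores. At k = 1 and r = 0.9 the ratio is 0.986, a gain of only 1%. At k = 1.25 and r = 0.8 it is 1.011, a slight loss. This stands as a caution, but the loss is bounded at about 1%.

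Third, the documents describe the paired test for before and after, not for A against B. If sites share a mouth and the unpaired test was used, part of any change would come from the pairing. This is fair. The 25-pair row measures only what the baseline term adds once pairing has been respected.

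Fourth, whether defects are independent may matter more: root-coverage p moves from 0.36 to 0.11 over the assumed within-pair correlations. That also stands, and it has to be settled before the model is fixed. An interval for the arm difference is likewise needed with or without a covariate. Lastly, the flooring simulation covers only the case of no treatment effect, so CI coverage for RD under a real difference was not examined.

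**Conclusion.** The point holds. The statistical text describes no baseline-adjusted arm comparison for RD, RW, CAL or WKG, and all four were measured at baseline. Against a test on 6-month values with independent defects, ANCOVA would change the CI width by +1% to −28% for r from 0 to 0.7. It gains whenever r exceeds about 0.15, or about 0.22 in a 25-pair design. For RD the corresponding range is +1% to −24% with a quarter of values at zero and +1% to −19% with half. Against change scores the gain is 7–28% at equal SDs and about 50% if the 6-month SD is half the baseline SD. It shrinks to nothing, with at most a 1% loss, when the slope on baseline is near 1.

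Every r, SD ratio and share of zeros is an assumption. The change is worth making, but the t-tests are not invalid and nothing here shows that a reported conclusion would change.

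**What to change.** State first how many patients contributed the 50 defects, and whether sites A and B lie in the same mouth. Then, for each of RD, RW, CAL and WKG, compare arms at 6 months by ANCOVA with the defect's own baseline value as covariate. Report the adjusted difference with its 95% CI, labelled post hoc because results are already reported. If any patient gave more than one defect, or the sites share a mouth, put the patient in that same model. With one A and one B site per mouth, this means regressing the 6-month A−B difference on the baseline A−B difference, with the intercept as the arm effect. Keep percentage root coverage as reported and add its difference and 95% CI, computed for whichever design applies.

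The cost is revised analysis wording and a rerun on existing data, with no new patients, visits or measurements. Each model spends one degree of freedom on the covariate. If r is 0, the CI is expected to be about 1% wider (about 2% with 25 pairs).

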### **Student's t-test:**

When sample size is small, 't' test is used to test the hypothesis. This test was designed by **W. S. Gossett**, whose pen name was '**Student**'. Hence this test is also called 'Student's t-test'.

$t = \text{ratio of observed difference between two means of small samples to the standard error of difference in the same.}$

It is applied to find the significance of difference between two proportions as,

1. Unpaired 't' test
2. Paired 't' test

### **Criteria for applying 't' test,**

1. The sample must be randomly selected.
2. The data must be quantitative.
3. The variable is assumed to follow a normal distribution in the population.
4. Sample should be less than 30.

## **Unpaired (independent) 't' test:**

This test is applied to unpaired data of independent observations made on individuals of two different or separate groups or samples drawn from two populations, to test if the difference between the means is real or it can be attributed to sampling variability.

### **Steps:**

1. As per the null hypothesis, assume that there is no real difference between the means of two samples.
2. Find the observed difference between means of two samples ( $\bar{X}_1 - \bar{X}_2$ )
3. Calculate the standard error of difference between the two means.

$$SE = \sqrt{\frac{1}{n_1} + \frac{1}{n_2}}$$

4. Calculate the 't' value

$$t = \frac{\bar{X}_1 - \bar{X}_2}{SE}$$

5. Determine the pooled degrees of freedom from the formula

$$d.f. = (n_1 - 1) + (n_2 - 1) = n_1 + n_2 - 2$$

6. Compare calculated value with the table value (table of 't') at particular degrees of freedom to find the level of significance.

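### Does the unpaired t-test's printed standard error, which has no standard deviation in it, put the between-arm comparisons at risk?

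*Combined protocol and SAP*

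**What the plan says.** The Statistical Analysis section of the combined protocol and SAP gives the method in a few lines: "Statistical analysis of the data was done using the statistical package for the social science (SPSS 22.0"), with Student's paired and independent t-tests at the 5% level. General subsections on the t-test follow.

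- *Student's t-test* defines t as "ratio of observed difference between two means of small samples to the standard error of difference in the same".
- *Unpaired (independent) 't' test*, Steps: step 3 reads "Calculate the standard error of difference between the two means" and prints SE = √(1/n1 + 1/n2). Step 4 divides the mean difference by that SE. Step 5 reads "Determine the pooled degrees of freedom from the formula", giving n1 + n2 − 2. Step 6 refers the result to a t table.
- *Paired t test*, Steps: step 4 reads "Work out the standard error of mean" and prints SD/√n, so here the standard deviation is present.

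The Abstract gives the arms as "PRF membrane (site A, n = 25 defects") and "CAF with chorion membrane (site B, n = 25 defects"). It reports six-month root coverage of 86.76 ± 13.76 and 82.89 ± 15.65 per cent, "with no statistically significant difference between them".

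**The concern.** A standard error of a difference in means must carry the variability of the outcome. The printed one does not, so the resulting ratio changes with the unit of measurement and does not follow a t distribution on n1 + n2 − 2 degrees of freedom. The unpaired test is the between-arm comparison, which is the trial's main question. If someone worked from the printed steps, an outcome with a large standard deviation would nearly always come out significant, and one with a standard deviation well below 1 nearly never. The unpaired and paired subsections also disagree on whether a standard deviation belongs in the formula. It is therefore reasonable to ask whether any reported between-arm result was produced this way.

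**Working it through.** **Inputs.** From the Abstract: n1 = n2 = 25; means 86.76 and 82.89; the figures after ±, 13.76 and 15.65, read as standard deviations because the Statistical Analysis section says that mean and standard deviation were calculated for each variable. Significance level 0.05, also from that section. The section does not state sidedness, so two-sided is assumed. Defects are taken as independent.

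**1. Reproduce the reported result with the standard pooled test.**

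- Difference = 86.76 − 82.89 = 3.87 percentage points.
- Sp² = (24 × 13.76² + 24 × 15.65²)/48 = (189.34 + 244.92)/2 = 217.13, so Sp = 14.74.
- SE = Sp × √(1/25 + 1/25) = 14.74 × 0.2828 = 4.168.
- t = 3.87/4.168 = 0.929 on 48 df, p = 0.358. The Welch version also gives p = 0.358.

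This agrees with the Abstract's non-significant result.

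**2. Apply the printed line literally.**

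- SE = √(1/25 + 1/25) = 0.2828.
- t = 3.87/0.2828 = 13.68 on 48 df, p = 3.5 × 10⁻¹⁸.
- The critical value on 48 df is 2.011, so any difference above 2.011 × 0.2828 = 0.569 points would be called significant.

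This contradicts the Abstract.

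**3. Dependence on units.** The root-coverage formula on the proforma has no multiplication by 100. On a fractional scale the printed line gives t = 0.0387/0.2828 = 0.137 and p = 0.89, while the pooled t stays at 0.929. The field is labelled as a percentage and the Abstract reports percentages, so step 2 is the relevant comparison.

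**4. How far wrong the printed line would be in general.** Under no true difference and a common standard deviation σ, the printed ratio is normal with mean 0 and standard deviation σ. Its two-sided type I error is then 2 × P(Z > 2.011/σ). Apart from 14.74, the σ values below are illustrative, because the documents give standard deviations for root coverage only.

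| σ | Type I error |
|---|---|
| 0.5 | 0.006% |
| 0.8 | 1.2% |
| 1 | 4.4% |
| 1.5 | 18% |
| 2 | 31% |
| 14.74 | 89% |

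The error runs in either direction and nearly vanishes at σ = 1. It is not a uniform fault across outcomes.

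**5. Which text governs.** The Statistical Analysis section describes, in the past tense, an analysis done in named software with a named test. SPSS derives the standard error from the data, and the user does not supply a formula for it. The later subsections explain where the name Student comes from, when a t-test may be used, and how to look up a table. None of them mentions an arm, an outcome or a visit of this trial. The definition of t, the degrees of freedom in step 5 and the paired formula all point to the usual pooled test.

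**The case for a change.** The strongest reply is that these subsections are the only detailed account of the test, that step 6 sends the reader to a printed table as if working by hand, and that nothing says the software output takes precedence. The agreement in root coverage also settles only root coverage. For recession depth and width, attachment level, keratinised width, plaque index and gingival index, the documents give no standard deviations, t values or p values. If their standard deviations were small, the printed line would also tend to return a non-significant result, so the reported findings cannot tell the two formulas apart. Finally, a symbol lost in reading the PDF would not fully explain why no step tells the reader to compute a standard deviation.

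Part of this stands. As extracted, the line is wrong, and the other outcomes cannot be checked from the documents. What does not follow is that the line was ever used. No hand-calculated test is reported, the stated method is a software procedure, and the one comparison that can be checked points away from the printed formula. A primer that skips an intermediate quantity is incomplete teaching text. It does not set a different test for the trial.

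**Conclusion.** No change to the plan follows. The missing pooled standard deviation is a notation slip in explanatory text, and a symbol lost in PDF reading cannot be excluded. Any analyst told to run an independent t-test in SPSS gets the right standard error whatever that line says. The contrast between p = 0.36 and p < 0.0001 is arithmetically correct, but it describes a calculation that the reported root-coverage result indicates was not done. Restoring the symbol would change no analysis, result or conclusion.

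This rests on a two-sided test, 25 defects per arm analysed at six months, ± meaning standard deviation, and independent defects. The last is not established, because the documents give no patient count. If the two sites were paired within patients, the unpaired test would not apply. Over assumed within-patient correlations of 0, 0.5, 0.75 and 0.9, the paired p value (24 df) would be 0.36, 0.20, 0.079 and 0.009. That is a separate question about the design. The missing symbol has no bearing on it, since the paired formula as printed does include the standard deviation.
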